## 2 RATIONALE

Mechanisms of shoulder instability, and the subsequent development of arthritis, are poorly understood (Deitch, Mehlman et al. 2003, McFarland, Kim et al. 2003, Barden, Balyk et al. 2005, Barrett 2015). Both surgical and nonsurgical interventions are based on a current understanding of the associated mechanisms that may include anatomical predisposition (shallow glenoid, lax ligament and capsule), weak muscles, or inappropriate muscle coordination (Harryman, Sidles et al. 1992, Cordasco 2000, Inui, Sugamoto et al. 2002, Deitch, Mehlman et al. 2003, McFarland, Kim et al. 2003, Barden, Balyk et al. 2005, Hovelius and Saeboe 2009, Jaggi and Lambert 2010, Jaggi, Noorani et al. 2012, Barrett 2015, Longo, van der Linde et al. 2016, Bateman, Jaiswal et al. 2018, Best and Tanaka 2018).

Rehabilitation approaches are preferred over surgical methods for the growing child, and management is therefore aimed at addressing predominant factors associated with these mechanisms e.g. exercises to improve co-ordination of the shoulder muscles if the source of instability is dysfunctional muscle control. However, failure rates are high (approximately 70% - 90%), indicating that current understanding of these mechanisms is limited.

In children, this can have detrimental long-term effects. This research is important as shoulder instability, mainly subluxation and dislocation, is common (23.9/100,000 person years but can be as high as 164.4 for 14 -16 year olds) (Leroux, Ogilvie-Harris et al. 2015) resulting in pain, decreased movement and functional limitations. Diagnosis of shoulder instability is normally delayed (on average by 2-years) and 70% of children have repeated dislocations (Longo, van der Linde et al. 2016), often associated with premature glenohumeral arthropathy (odds ratio 19.3) (Marx, McCarty et al. 2002, Deitch, Mehlman et al. 2003).

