### 3 OBJECTIVES AND OUTCOME MEASURES/ENDPOINTS

#### 3.1 Primary objective

- The primary objective of this study is to identify factors responsible for recurrent shoulder instability in children.

In order to meet the main objective of this study, a series of secondary objectives need to be met.

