#### **4 STUDY DESIGN**

This is an observational, cross-sectional study of children (aged 8 to 18) presenting with shoulder instability of any origin, traumatic or atraumatic (n=15) and an age-matched sample (n=15) with no history of shoulder problems. Muscle activity and movement pattern differences will be measured using non-invasive 3D motion capture and surface electromyography, to identify factors responsible for instability. Only a single visit to the site will be required (ORLAU, RJAH). No interventions or treatments are included in this study as this is an observational, cross-sectional study.

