## **6 ELIGIBILITY CRITERIA**

### **6.1 Children with shoulder instability**

#### **6.1.1 Inclusion criteria**

- Children aged between 8 to 18 years of age
- Subjective reports of instability with additionally symptomatic instability in the clinical assessment criteria below
- Symptomatic instability on clinical assessment in at least one direction, confirmed by a positive clinical finding (apprehension, guarding, laxity) during the sulcus, apprehension or anterior and posterior shift load tests.
- All forms of instability including multidirectional instability, atraumatic and traumatic subluxations and dislocations.
- Children presenting with an initial or recurrent episode of instability
- Children undergoing current management or rehabilitation for their shoulder at the time of the study
- Patients with surgically managed shoulder instability who have since had a further episode of shoulder instability.

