### 7.1.4 Shoulder stability tests for age matched controls (not for screening)

	CRITERIA	YES	NO	Type e.g. (L)
1.	Please make note of any clinical findings of - Apprehension (A) - Guarding (G) - Laxity (L)	1a. Sulcus (inferior) 1b. Anterior shift load 1c. Posterior shift load 1d. Apprehension relocation		

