### 7.5 Nine point Brighton hypermobility score

One point is given for each of the side and test

	TEST DESCRIPTION		SCORE
B1.	Passively extend the fifth metacarpophalangeal joint $\geq 90^\circ$	L	
		R	
B2.	Passively oppose the thumb to the anterior aspect of the forearm	L	
		R	
B3.	Passively hyperextend the elbow to $\geq 10^\circ$	L	
		R	
B4.	Passively hyperextend the knee to $\geq 10^\circ$	L	
		R	
B5.	Actively place hands flat on the floor without bending the knees	L	
		R	
		Total	/9

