  - i) data from study objective 2 will be evaluated to identify features i.e. movement or muscle activity patterns, which may be used to categorise clinical presentations of shoulder instability. An appropriate clustering/categorisation method will be selected once the characteristics of the dataset has been established

if we get a large enough sample size of participants with a homogenous clinical presentation and if three or more groups are identified in the preceding work package, an analysis of variance (ANOVA) can be used. For less than three groups, an independent sample t-test will be used.

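### Laxity is measured but has no role in the analysis, and objective 3 looks only at movement and muscle features, so laxity cannot emerge as a factor and its effect can be read as a movement factor

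*Combined protocol and SAP*

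**What the plan says.** - **Aim.** Section 3.1: "The primary objective of this study is to identify factors responsible for recurrent shoulder instability in children".
- **Mechanisms.** Section 2 lists the candidates as "anatomical predisposition (shallow glenoid, lax ligament and capsule), weak muscles, or inappropriate muscle coordination".
- **Generalised laxity.** Section 7.5, headed "Nine point Brighton hypermobility score", scores five tests on the little finger, thumb, elbow, knee and trunk. It is not restricted to either group.
- **Shoulder laxity.** Sections 6.1.1 and 7.1.2 make laxity on a sulcus, apprehension or shift-load test one of three findings that can qualify a child as a case. Section 7.1.4 records the same findings in controls but states that they are not used for screening.
- **Controls.** Section 4 describes "an age-matched sample (n=15) with no history of shoulder problems". Age is the only matching factor.
- **Analysis.** Section 8.3 summarises kinematic and kinetic data descriptively and lists the EMG measures. Objective 3 then states that "data from study objective 2 will be evaluated to identify features i.e. movement or muscle activity patterns", to be used to categorise presentations. The clustering method is left open. A t-test or ANOVA is mentioned for the resulting groups, conditionally and without a covariate.

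**The concern.** Objective 3 is where the study identifies factors for recurrence, and its inputs are limited to objective 2 data. One of the mechanisms in the plan's own rationale is thus excluded from the search, although two sets of laxity data are collected.

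The design makes a laxity difference between cases and controls plausible. Laxity can qualify a case, multidirectional and atraumatic instability are included, and controls are neither matched nor screened on laxity. Maximal flexion and abduction are core tasks, and section 8.3 reports range of movement. A laxer child may simply move further. If so, a case-control difference in range could be described as a movement pattern linked to instability when it partly reflects laxity. Section 1 hopes that the study may show for which children physiotherapy is unsuitable, and that reading depends on keeping the two apart.

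**Working it through.** **1. Tracing laxity through the document**

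| Place | Role of laxity |
|---|---|
| Section 2 | Named mechanism |
| Sections 6.1.1, 7.1.2 | Can qualify a case |
| Section 7.1.4 | Noted in controls, not used to select them |
| Section 7.5 | Hypermobility score recorded |
| Study summary, sections 3.1 and 3.2 | Absent |
| Section 8.3 | Absent; objective 3 inputs are movement and muscle features only |

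The plan states no effect size, SD or power to reproduce. Section 8.1 says that a power calculation is not possible.

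**2. Size of a possible misreading (all inputs assumed)**

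Let p1 and p0 be the proportions hypermobile in cases and controls, and R the extra range in a hypermobile child. The case-control difference due to hypermobility alone is D = (p1 − p0) × R. Assume p1 = 40–60%, p0 = 10–20% and R = 10–20 degrees.

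- Low end: (0.4 − 0.2) × 10 = 2 degrees.
- High end: (0.6 − 0.1) × 20 = 10 degrees.

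D is zero if the groups do not differ in laxity or if laxity does not affect range. The formula covers case-control range of movement only. It says nothing about categories within the instability group or about EMG.

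**3. Illustrative simulation**

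This used 20,000 studies of 15 per group, with a movement variable that depends on laxity (within-group correlation r) and has no group effect of its own. With a laxity difference of 1.0 SD and r = 0.5, the apparent difference is 0.5 × 1.0 = 0.50 SD. An unadjusted 5% t-test was then significant in 26% of studies, against 5% after adjustment. With no laxity difference the unadjusted rate stayed at 5%. The simulation shows the mechanism; it does not estimate this study's error rate, because section 8.3 does not clearly specify a case-control t-test.

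**4. Price of adjustment**

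With equal groups, the correlation between group and a yes/no hypermobility indicator is φ = 0.5 × (p1 − p0) / √[p̄(1 − p̄)], where p̄ is the mean prevalence. The group standard error is multiplied by 1/√(1 − φ²) before any gain from lower residual variance.

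- 60% v 10%: φ = 0.25/√(0.35 × 0.65) = 0.52; multiplier 1/√(1 − 0.275) = 1.17, about 17% larger.
- 40% v 20%: φ = 0.10/√(0.30 × 0.70) = 0.22; multiplier 1/√(1 − 0.048) = 1.02, about 2% larger.

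The residual gain can outweigh this. In the simulation with a 1.0 SD laxity difference, the unadjusted standard error is √(2/15) = 0.365. The mean adjusted one was 0.396 at r = 0.3 and 0.297 at r = 0.7.

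**5. The score form**

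Section 7.5 says "One point is given for each of the side and test". Five tests on two sides give 5 × 2 = 10 boxes, yet the total is out of 9, because the trunk test has a left and a right row. This may be a table-reading artefact. The section heading says Brighton where the table of contents says Beighton.

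**The case against.** **The bias is conditional.** A reader might infer that a laxity effect will be reported as a movement or muscle factor. The documents do not support that. It needs both a laxity difference between the compared groups and a link between laxity and the variable, and neither is quantified. The muscle half is weaker still, since nothing in the plan shows how hypermobility would change EMG presence, onset, percentage of maximum or time of peak.

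**The study is small and largely descriptive.** This stands. Section 8.3 compares groups by means and SDs, and its tests depend on groups yet to be derived. At 15 per group, 80% power needs a difference of about 1.06 SD, so a laxity effect may also be missed. But tabulating laxity and listing it as a candidate needs no test.

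**The score does not measure the shoulder.** Also true, which is why the shoulder findings belong in the fix. They are a poor covariate for case-control comparisons, however, because a positive finding helps to define a case.

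**Laxity may act through movement.** Adjustment could then remove a real pathway. This stands, and it rules out treating a feature as a distinct factor only if it survives adjustment. With 30 children, neither survival nor disappearance would settle the question.

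**Other variables are unused too.** Side, direction and number of previous episodes (section 7.4) also have no analysis role. Laxity differs in that section 2 names it as a mechanism.

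**Conclusion.** The gap is real and worth closing before analysis. Followed as written, section 8.3 cannot return laxity as a factor. It also offers no planned way to see whether a case-control difference in range of movement partly reflects laxity.

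The size is unknown. The 2 to 10 degrees rests wholly on assumed prevalences and an assumed effect on range. Section 8.1 says that the standard error of measurement is unknown, so one cannot say whether 2 degrees would be distinguishable from measurement error.

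Two stronger readings should be resisted. One is that the study cannot separate laxity from movement at all: the data are collected, so the analysis remains possible. The other is that separating mechanisms for referral is a stated objective: section 1 presents it as a possible benefit, and sections 3.1 and 3.2 do not list it.

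**What to change.** Amend section 8.3 as follows.

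1. Report the hypermobility score and the shoulder laxity findings from sections 7.1.2 and 7.1.4 by group, and for any category derived under objective 3. Shoulder findings in cases should be read with the entry criteria in mind.
2. Add both to the candidate features in objective 3, beside the movement and muscle features.
3. Show case-control differences in range of movement with and without the hypermobility score as a covariate, labelled exploratory. State that the adjusted estimate may remove a real pathway and may be less precise. Do not make persistence after adjustment a condition for calling something a factor.

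Before the score is used, reconcile the form in section 7.5 (ten boxes against a total of 9, and the name of the score) and confirm that it is completed in both groups. Check also that the case form in section 7.1.2 records which finding was positive: the control form has a column for the type, and the case form, as it reads here, does not.

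The cost is plan wording and a form check, with no extra visit or measurement. Adjustment uses one degree of freedom. It may also widen the group standard error, by about 17% at 60% v 10% prevalence before any residual-variance gain.

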## 9 DATA HANDLING

### 9.1 Data collection tools and source document identification

All documents and information are confidential and will be handled and safeguarded in the manner that ensures privacy and confidentiality of participant's personal information, in compliance with Data Protection Act (2018).

All documents and forms containing participants' personal information will be safeguarded and stored on-site at either Robert Jones Angus Hunt Hospital (RJAH) main building or The Orthotic Research & Locomotor Assessment Unit (ORLAU) building in RJAH. Only authorised individuals involved in this study will have the right to access these documents and information. Any electronic participants' information and/or data will only be stored in an NHS secured laptop, with two-factor authentication access. Then, these will be transferred to RJAH hospital servers. Finally, the study team and associated institutions will have access to anonymised data only. Only anonymised data will be transferred to an encrypted university laptop.

### 9.2 Data handling and record keeping

This data management plan was developed ensure that data of this research is managed and shared in a robust and professional manner. The plan was formulated with adherence the United Kingdom Research and Innovation Data Policy, RJAH Hospital Trust Data Protection, Data Protection Act 2018 and General Data Protection Regulation 2018.

All forms, documents, and templates will be stored within ORLAU at RJAH. ORLAU building access is restricted by a reception desk and a password-protected locked door. Any electronic data of participants will also be copied and saved onto RJAH servers, which are protected under NHS electronic security. The research team will only have access to the participant NHS records once the participant has been consented for the study.

---

 Available at, respectively; <https://goo.gl/muBtwD>; <https://www.rjah.nhs.uk/Patient-Visitors/Data-Protection.aspx>; <https://www.legislation.gov.uk/ukpga/2018/12/contents/enacted>; <https://ico.org.uk/for-organisations/guide-to-data-protection/guide-to-the-general-data-protection-regulation-gdpr/>

Once the study is concluded, all appropriate paper-based forms of participants will be moved and stored in a locked cabinet at ORLAU for 10 years, then they will be destroyed.

Confidentiality and anonymity will be maintained for all participants. Any identifying information provided (e.g. names and addresses) will be held in the strictest confidence and stored in a confidential, password protected database accessible by only those with permission. All data used for analysis will be kept separate from participant personal data. Hard copy material (e.g. signed consent forms) will be stored securely for a minimum period of 10 years after the study has been completed. After that period all hard copy material will be reviewed, and approval for destruction from the sponsor will be sought. All study participants will be allocated a unique identification number, therefore, making it possible to anonymise research data. All sensitive datasets will be retained on a secure server and access restricted to the study team. Access to all research datasets is controlled by password protection and additional permissions specific to folders.

All confidentiality arrangements adhere to relevant regulations and guidelines (General Data Protection Regulation 2018, Data Protection Act 2018, General Medical Council (GMC), Medical Research Council (MRC), Research Governance Framework) and the chief investigator has a responsibility to ensure the integrity of the data and that all confidentiality procedures are followed

### **9.3 Access to Data**

Only members of the ORLAU clinical team, students and clinical supervisors will have access participants' personal data for the duration of the study. The principal investigator is already part of the direct healthcare team on-site. Other members of the research team will only have access to anonymised data. Members of staff from the sponsor and/or regulatory bodies may also require access to study participant's data in order to carry out audits. All these staff work to robust data security procedures.

The raw data will be generated and stored electronically on an NHS-secured computer. Only anonymised data will be transferred to an encrypted university laptop. The researcher, academic supervisor, the principal investigator and clinical supervisors will be involved in the analysis of data. Other members of the research team will only have access to anonymised data. The anonymised dataset will be stored on the University of Liverpool data repository, the anonymised data will be openly available.

---

 <http://datacat.liverpool.ac.uk/>

Paper-based data will be stored at RJAH in a locked cabinet, and Electronic data will be stored on RJAH hospital Trust servers, which have restricted access by a two-way authentication procedure. Paper-based data will be kept on-site for 10 years and will be destroyed after the sponsors approval. [name] is the custodian of the data, as she is the manager of ORLAU. ORLAU entrance is restricted by a reception desk and a locked door with passcode keypad. Accessibility to these data is governed by RJAH local hospital policies and. RJAH is the sponsor of this study, which makes it the owner of the data generated by this study, All of these guidelines are implemented to ensure these arrangements are in compliance with the Data Protection Act 2018, GDPR 2018 and Research Governance Framework.

#### **9.4 Data Sharing Agreements**

The anonymised final trial dataset and anonymised 3D movement data files will be stored on the University of Liverpool and RJAH Data repositories where they will be assigned a Digital object identifier. The anonymised data will be openly available.

#### **9.5 Archiving**

Study related data will be stored as per RJAH hospital policies, which are compliant with the NHS Retention schedules reported in Records Management Code of Practice for Health and Social Care 2016. Secondary anonymised data will be reported in the following data repositories:

- RJAH
- University of Liverpool

In addition, the secondary anonymised data may be presented in a thesis, which will be archived as per University of Liverpool guidelines.

Paper-based data will be kept on-site for 10 years and will be destroyed after the sponsors approval. [name] is the custodian of the data, as she is the manager of ORLAU. Accessibility to these data is governed by RJAH local hospital policies. RJAH is the sponsor of this study, which makes it the owner of the data generated by this study.

---

 Available at: <https://digital.nhs.uk/binaries/content/assets/legacy/pdf/n/b/records-management-cop-hsc-2016.pdf>

## **10 MONITORING & AUDIT**

### **10.1 Safety Reporting**

A complication of shoulder instability is increased risk of further episodes of shoulder instability. In order to minimise the risk, for children with shoulder instability the first assessment will be conducted a minimum of 12 weeks from their most recent episode of instability. This time point has been selected from experience in managing this patient group and after further discussion with our clinical partners to identify a suitable time point which minimises the risk of recurrent instability, ensures the measurements do not exacerbate participant symptoms and allows them to complete the required tasks. The movement tasks for analysis have also been selected to minimise any risks of instability.

We do not anticipate participants as having episodes of instability during the measurement sessions. However, if participants do suffer a dislocation during the measurement session which does not spontaneously reduce/resolve, there is emergency care available on site and the participant will be managed according to the RJAH hospital trust procedures. The principal investigator is already part of the direct healthcare team on-site. A monthly meeting with the research team will be regularly held to discuss the conduct of the study, including adverse events Safe practice and Risk Assessment.

## **11 ETHICAL AND REGULATORY CONSIDERATIONS**

The study will be submitted for approval by the HRA through which REC approval will be obtained. The study team will provide the REC with a copy of the final protocol, patient information sheets, consent forms and all other relevant study documentation as part of the HRA approval process. The chief investigator will ensure that REC approval is obtained prior to recruitment of any participants in the study. Before any site can enrol patients into the study, the Chief Investigator will ensure that appropriate approvals from participating organisations are in place.

For any amendment to the study, the Chief Investigator, in agreement with the sponsor will submit information to the appropriate body in order for them to issue approval for the amendment. The Chief Investigator will work with sites so they can put the necessary arrangements in place to implement the amendment and to confirm their support for the study as amended. Substantial amendments that require review by NHS REC will not be implemented until that review is in place and HRA approval obtained for the amendment.

All correspondence with the REC will be retained. An annual progress report (APR) will be submitted to the REC within 30 days of the anniversary date on which the favourable opinion was given, and annually until the study is declared ended.

The Chief Investigator will take overall responsibility to produce annual reports as required. Within one year after the end of the study, the Chief Investigator will submit a final report with the results, including any publications/abstracts, to the REC.

The Chief Investigator will notify the REC of the end of the study. If the study is ended prematurely, the Chief Investigator will notify the REC, including the reasons for the premature termination.

The following stages have been taken to address the ethical considerations and minimisation of measurement burden for our study, therefore ensuring the safety of participants.

A complication of shoulder instability is increased risk of further episodes of shoulder instability. In order to minimise the risk, for children with shoulder instability the first assessment will be conducted a minimum of 12 weeks from their most recent episode of instability. This time point has been selected from experience in managing this patient group and after further discussion with our clinical partners to identify a suitable time point which minimises the risk of recurrent instability, ensures the measurements do not exacerbate participant symptoms and allows them to complete the required tasks. The movement tasks for analysis have also been selected to minimise any risks of instability. Participants will also be informed that they may stop the movement activities should their symptoms or discomfort worsen during testing.

We do not anticipate participants as having episodes of instability during the measurement sessions. However, if participants do suffer a dislocation during the measurement session which does not spontaneously reduce/resolve, there is emergency care available on site and the participant will be managed according to the trust procedures.

To record participant's movements, markers and devices will be placed on the skin using hypoallergenic medical adhesive tape. This is routine clinical practice in movement analysis laboratories and those conducting data collection will be trained in the application and removal of the markers. Some discomfort may be experienced by participants during marker and device removal, in the worst case it would be equivalent to that of a plaster being removed.

A monthly meeting with the research team will be regularly held to discuss the conduct of the study, including adverse events Safe practice and Risk Assessment.

